
PURPOSE

We propose to conduct the first randomized controlled trial to test whether a cessation intervention in the PED setting can reduce caregiver smoking and decrease children's SHSe.

Primary Aim 1: To evaluate the efficacy of the SBIRT compared to Healthy Habits Control (HHC) condition. Primary outcomes are self-reported prolonged abstinence and point prevalence at 6-weeks and 6-months post-enrollment, validated in all participants via expired carbon monoxide and salivary cotinine. Secondary outcomes include number of cigarettes smoked, quit attempts, readiness to quit, and use of cessation resources.

Hypothesis 1: Caregivers who receive the SBIRT will have higher prolonged abstinence and point prevalence cessation rates compared to caregivers in the HHC condition.

Primary Aim 2: To evaluate the efficacy of the SBIRT on reducing children's SHSe. Outcomes are caregiver reports of total home/car smoking bans and reductions in SHSe (validated using salivary cotinine in children).

Hypothesis 2: Children of SBIRT caregivers will have higher total home/car smoking bans and lower home/car smoking exposure compared to children of HHC caregivers.

Primary Aim 3: To explore mediators and moderators of the SBIRT outcomes.

Hypothesis 3: The SBIRT intervention effect on prolonged abstinence and point prevalence cessation rates will be mediated by the caregiver's perception of the risk of smoking on their child's health and the caregiver's motivation to quit over time. The intervention effect will be moderated and attenuated by factors such as household smokers, financial strain, and low social support to quit.

Secondary Aim 1: To conduct a cost analysis to determine the numbers of SHSe-related PED visits and hospitalizations in children of caregivers in the SBIRT condition compared to children of caregivers in the HHC condition. This will provide a basis for a future, full-scale cost-benefit analysis.

Secondary Aim 2: Using the findings from this project and our prior research, we will develop a manual of operations and a comprehensive package of provider and patient materials that will be disseminated for use in other PEDs and EDs nationwide.

Secondary Aim 3: To quantify the prevalence and identify correlates of Cannabis Smoke Exposure and SHSe among SHS-exposed PED patients.

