3) Intervention Materials: To supplement the baseline intervention, we will provide free caregiver materials used in other healthcare setting (see appendix C). All or some of the materials listed in Appendix C will be provided to the caregiver, as applicable. These materials are downloadable from www.letsgo.org.^{68,91-93} The caregivers will receive email/mail/text messages (caregiver’s preference), for 12 weeks, reminding them of healthy lifestyle behaviors. At 6-weeks we will contact participants via phone calls, emails, text messaging, social media, and home visits to children and caregivers in the SBIRT and HHC condition to: 1) verify abstinence on 100% of caregivers who report that they have not smoked in the past 7 days via expired carbon monoxide testing and salivary cotinine, 2) obtain a follow-up salivary cotinine level on 100% of children to validate total smoking bans, and 3) complete assessment of outcomes. At 6 months, we will contact all caregivers via phone, text messaging, social media or email. Should the caregiver report abstinence and smoking bans, a home visit will be conducted to validate self-reported abstinence and total home smoking bans via salivary cotinine on the child and via expired carbon monoxide testing and/or salivary cotinine on the caregivers during home visits. Follow-ups may be conducted at CCHMC hospital if the participant already has a scheduled appointment at the hospital. If a home visit is not possible, the assessments will be conducted over the phone or via email. An approximately four week window for the follow-up assessments will be used.

At the study’s conclusion, the HHC group will be given brief information regarding resources for quitting smoking over the telephone. A script will be used by the research coordinator to provide this information.

Screening for missed eligible patients

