11. Clinical and cost data. We will be evaluating the clinical characteristics and associated costs/charges of the baseline visit and hospitalization (if the child is hospitalized) and any SHSe-related or other visits or hospitalizations for the period up to 12 months prior and/or 12 months after the baseline visit. We will extract clinical data and costs from the charts that may include data on the presenting illness and illness severity (e.g., heart rate, respiratory rate, oxygen saturation, physical exam findings, triage level, chief complaint, discharge diagnosis, disposition), lab tests, procedures, interventions, and test results (if any), during these visits and/or hospitalizations.

12.

Follow-up Assessments (Table 1). All participants will be assessed at 6-weeks (T1) during home visits and at 6-months (T2) via phone or email; home visits will be made to conduct biochemical validation of caregivers and children when caregivers report that they have quit at T2. We will use self-report measures of prolonged abstinence and biochemically validated point prevalence at T1 and T2 to assess cessation.⁸⁵⁻⁸⁷ Point prevalence of tobacco use will be measured by the question: “Have you smoked, even a puff, in the last 7 days?” Caregivers will be considered abstainers if they report no tobacco use in the past 7 days. Prolonged abstinence will be measured by the question: “When did you last smoke a cigarette?” Response categories will range from “less than 1 month ago” to “more than 6 months ago.” Secondary outcomes will be assessed, including nicotine dependence, readiness to change, a quit attempt of \geq 24 hours, patterns of smoking, number of cigarettes smoked/day, treatment initiation, NRT or other pharmacotherapies used, QL, text, or web follow-up. As described above, we will use measures of child SHSe to assess children’s exposure and if home/car smoking bans are present. Secondary outcomes pertaining to the child’s SHSe, total home/car smoking bans, and SHSe-related healthcare utilization (PED visits or hospitalizations at CCHMC) will be assessed.

Biochemical Validation. At 6-weeks, we will conduct home visits to: (1) verify abstinence on caregivers who report that they have not smoked in the past 7 days via expired carbon monoxide testing and salivary cotinine (2) obtain

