a follow-up salivary cotinine level on children to validate total home smoking bans, and (3) complete assessment of outcomes. Cotinine is generally accepted to be the best of the available biomarkers, with over 95% specificity and sensitivity, it is noninvasive, and easily obtained in young children.^{85,86} [ENREF 114](#) A standard protocol will be used to collect saliva samples from each child at baseline, 6-weeks, and possibly 6 months. Cotinine analyses will be performed with Enzyme Immunoassay techniques by Salimetrics LLC, State College, PA. In the child samples, the lower limit of cotinine sensitivity is 0.05 ng/ml (range of sensitivity: 0.06-200 ng/ml); undetectable cotinine values will be recorded as 0 ng/ml.^{87,88} Alternatively, if additional funds are available, cotinine analyses may be assessed with liquid chromatography mass spectrometry (LCMS). Caregiver abstinence will be established if the caregiver's expired carbon monoxide level is at or below 6 ppm; salivary cotinine may be assessed to confirm abstinence in caregivers who report they have quit if their exhaled carbon monoxide does not provide verification. At 6 months, we will assess all caregivers via phone or email, and validate self-reported abstinence and total home smoking bans via expired carbon monoxide testing and/or salivary cotinine.

Data Management

Data management will occur at CCHMC. Participants will complete the baseline assessment on a web-enabled tablet research computer. Data will be collected and managed using REDCap (Research Electronic Data Capture).⁹² [ENREF 116](#) The Redcap Mobile App may also be used in order to scan barcodes on samples.

DATA ANALYSIS

Sample Size and Power Estimates

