We will use GLMM to evaluate the relative effectiveness of the SBIRT versus HHC group on our primary outcomes: point prevalence and prolonged abstinence at 6-months. The analysis will be repeated with caregiver level differences between groups included as covariates. We will use mixed model analysis of covariance, with repeated measures to assess change (controlling for baseline differences between groups) to assess the effect of the SBIRT on secondary outcomes including reduction in use, number of quit attempts, and changes in readiness to quit. Kappa statistic will be used to assess agreement between the caregiver's self-report and the assessment of tobacco use based on expired carbon monoxide levels and/or salivary cotinine at 6 months. It is possible that use of and adherence to the NRT will influence outcomes in the intervention group. In addition, some of the participants in the control condition may obtain NRT during the study interval. We will examine NRT use or dose, defined as self-reported adherence, as a covariate in order to control for this possible relationship.

Analyses for Primary Aims 1-3.

Primary Aim 1, Hypothesis 1: We hypothesize that SBIRT participants will have higher prolonged abstinence and point prevalence cessation rates compared to those in the HHC group. As stated above, our primary approach to the analysis is using multiple imputation, with clinical counselors/intake coordinators/research coordinators included in the model. We shall then use analysis of covariance, to control for any baseline differences of caregivers between conditions. In addition we will also control for motivation to quit, considered a priori as a potential covariate, using the score on the contemplation ladder. As we are stratifying on motivation to quit and caregiver gender, we will initially enter this into the model as an interaction. To address child cotinine as the 6-month outcome, we will use a t-test and then an analysis of covariance to incorporate the variables different at baseline. Incorporating the 6-week outcome values, we will use GLMM invoking GEE for the repeated

measures and also a model including covariates. This approach will be used to assess the intervention's effect on abstinence and point prevalence and child cotinine.

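### The protocol defines the primary abstinence outcomes in conflicting ways and never says whether the self-reported or the verified variable enters the primary analysis

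*Combined protocol and SAP*

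**What the plan says.** The relevant statements are spread over several sections of the combined protocol and SAP.

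- **Purpose, Primary Aim 1.** Prolonged abstinence and point prevalence at 6 weeks and 6 months are self-reported and "validated in all participants via expired carbon monoxide and salivary cotinine".
- **Follow-up Assessments (Table 1).** The general statement is "We will use self-report measures of prolonged abstinence and biochemically validated point prevalence at T1 and T2 to assess cessation". The rule for the 7-day question follows: "Caregivers will be considered abstainers if they report no tobacco use in the past 7 days". Prolonged abstinence rests on one item about when the last cigarette was smoked. Its answers run from under one month to over six months, and no cut-off is given.
- **Biochemical Validation.** "Caregiver abstinence will be established if the caregiver's expired carbon monoxide level is at or below 6 ppm". Salivary cotinine may be used when CO does not confirm a reported quit.
- **Healthy Habits Control Condition, Intervention Materials.** "If a home visit is not possible, the assessments will be conducted over the phone or via email". The NRT paragraph of the SBIRT Protocol likewise allows a phone or email survey at 6 weeks, with a mailed sample.
- **Analytic Plan.** The model is applied to "our primary outcomes: point prevalence and prolonged abstinence at 6-months", without saying self-reported or verified. Agreement between self-report and the biochemical classification is assessed by kappa. Multiple imputation is the stated primary approach for Hypothesis 1.

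**The concern.** A primary outcome needs one classification rule. Here a caregiver who reports not smoking but fails the test, or never has one, is abstinent under the Follow-up Assessments sentence and is not established as abstinent under the Biochemical Validation sentence. Nothing in the Analytic Plan breaks the tie. The kappa analysis confirms that two separate variables will exist. If the choice is made after the data are seen, it can decide the result.

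The choice also affects bias. SBIRT caregivers are advised to quit and offered NRT and referral, while HHC caregivers get diet and activity advice. A false claim of quitting may therefore be more common in SBIRT, and a self-report classification would turn that difference into apparent benefit. Prolonged abstinence is the more exposed of the two outcomes, because Follow-up Assessments describes it only as self-report.

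**Working it through.** **Passages side by side**

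| Outcome | Primary Aim 1 | Follow-up Assessments | Biochemical Validation | Analytic Plan |
|---|---|---|---|---|
| Point prevalence | validated in all | labelled validated, classified on report | CO at or below 6 ppm, cotinine back-up | not stated |
| Prolonged abstinence | validated in all | self-report | same abstinence rule, measure not named | not stated |

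No section classifies a reported quitter with a failed or missing test. A CO reading cannot be posted, so the phone, email and mail routes imply some reported quitters without one. The 6-month visit trigger also varies: the Assessments paragraph and the HHC text ask for a report of abstinence and smoking bans, while Follow-up Assessments asks only for a report of quitting.

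**Inputs.** From Sample Size and Power Estimates: 300 per arm after 20% loss; HHC rates of 6.3% (point prevalence) and 2.1% (prolonged abstinence); SBIRT rate of 12% (point prevalence). Assumed, because the protocol gives no figure: two-sided alpha 0.05, false-claim rates, share of claims untested, share of reported quitters verified.

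**The plan's own figure.** The plan states 80% power for a 6.4-point increase (6.3% vs 12.7%) at 300 per arm. The pooled normal approximation gives 76.3%. That gap is a separate matter, and nothing below depends on it. For the planned 6.3% vs 12% the same method gives 67.9%.

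**False positives under over-reporting, no true effect.** Let q be the true quit rate, f the share of smokers who falsely claim to have quit, and u the share of claims untested. Suppose tests catch every false claim and pass every true quitter, and untested claims count as reported. The observed rate is q + (1 − q) × f × u.

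With q = 6.3%, u = 1 and f = 3% vs 1%:
- SBIRT: 0.063 + 0.937 × 0.03 = 9.1%
- HHC: 0.063 + 0.937 × 0.01 = 7.2%

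The pooled two-proportion z-test then rejects 13% of the time. The other cases follow in the same way:

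| q | Claims untested (u) | f = 3% vs 1% | f = 5% vs 2% |
|---|---|---|---|
| 6.3% | 100% (no test used) | 13% | 21% |
| 6.3% | 50% | 7% | 10% |
| 6.3% | 20% | 5.4% | 5.8% |
| 2.1% | 100% (no test used) | 23% | 35% |

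With equal false claims (3% in each arm) rejection stays at 5%.

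**Effect on power and on a single data set.** Treat 6.3% vs 12% as self-reported rates and let a share v of reported quitters verify in each arm. Power at 300 per arm is 67.9% at v = 1, 57.3% at v = 0.8 (5.0% vs 9.6%) and 38.6% at v = 0.5 (3.2% vs 6.0%). In counts, 19 vs 36 quitters by report gives p = 0.016. If 10 vs 18 are verified, p = 0.12. At v = 1 the two definitions agree.

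**The case against.** The strongest reply is that point prevalence is meant to be verified. Follow-up Assessments calls it biochemically validated shortly before the self-report sentence, Primary Aim 1 agrees, and reported quitters are to be tested at 6 weeks and 6 months. On that reading the question screens and CO confirms. This is probably the intention, and a reader who inferred that point prevalence is simply a self-report endpoint would go too far. It does not remove the conflict: the sentence that classifies caregivers omits the test, the primary model names no variable, and failed or missing tests have no rule. Prolonged abstinence gets no such help from its own section.

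A second reply is that 13% and 21% exaggerate the risk. That stands: they apply only if every test result is ignored. With planned testing largely done, the inflation is small.

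A reader might also infer that the top answer category, over six months, is impossible for someone who smoked daily at enrolment. The documents do not support this. Follow-up has a window of about four weeks, so a caregiver who quit at enrolment and is assessed late could give that answer truthfully. The 6-week and 6-month instruments are only listed as appendices, so the options at 6 weeks cannot be checked either.

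Finally, scoring every untested quitter as smoking is not automatically safe. SBIRT caregivers can receive more NRT at the 6-week visit, so completion of testing may differ by arm. If 90% vs 70% of quitters were tested (an assumption), 6.3% true quitting in both arms would appear as 5.7% vs 4.4%, and the test would reject about 11% of the time.

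**Conclusion.** The concern holds in a limited form. The definitions of both primary abstinence outcomes conflict, and the analysis plan does not resolve them. The same data can give different primary results; they need not, and will not if every reported quitter is tested and passes.

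Under the assumed false-claim rates, the false-positive risk for point prevalence runs from close to nominal (5-6% with 20% of claims untested) to 13% or 21% (no test used). For prolonged abstinence taken as self-report at the 2.1% rate it is 23% or 35%. These figures rest on over-reporting being more common in SBIRT, which is plausible from the design but not documented, and on an unstated alpha taken as two-sided 0.05. They illustrate the exposure and do not estimate the trial's actual error rate. The textual conflict does not depend on them.

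**What to change.** Amend Primary Aim 1, Outcome Measures, Follow-up Assessments and the Analytic Plan so that they carry one definition.

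1. Define the 6-month primary outcomes as self-reported abstinence plus verification by the Biochemical Validation rule: CO at or below 6 ppm, or cotinine where CO does not verify. State the caregiver cotinine cut-off, which the protocol does not give, and settle whether the two tests are joined by and or by and/or.
2. Count a reported quitter who fails verification as not abstinent.
3. State one primary handling of reported quitters with no test that is consistent with multiple imputation, for example imputing verified status. Show untested-as-smoking and self-report alone as sensitivity analyses.
4. For 6-month prolonged abstinence, combine the last-cigarette item with verified abstinence at 6 months and state the category cut-off. The item is collected in categories, so a rule that needs an exact quit date would require a new question.
5. Use one trigger for the 6-month verification visit.

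The cost is mainly wording, because the tests are already planned. The real downside is lower observed quit rates and lower power than under self-report. If only half of reported quitters verified (an assumption), power for 6.3% vs 12% would fall from 68% to 39%, so the power statement should say which definition it assumes.

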Sample Size. Our estimate of the number of caregivers that we plan to enroll is based on the average number of unique patients and the smoking prevalence of caregivers seen in a 12-month period in the PED at CCHMC. Based on enrollment in previous studies (which had average annual enrollment of 300-350 caregivers), and a 30 month chart review on the number of annual visits for patients with SHS-related complaints (at least 6,000), we are conservatively expecting to enroll 300 caregivers who smoke over 12 months, for a total of 750 caregivers in 30 months. To obtain the effective sample size for power analyses of outcomes, the sample size must be adjusted for potential attrition of approximately 20% at 6 months, although all efforts will be used to decrease this attrition rate, leaving a total of 600; 300 per group.

Estimate of effect sizes: Evaluation of outcomes. Based on the recommendations of Hughes et al.,^{85,86} we will use 2 criteria for abstinence: 6-month point prevalence and prolonged abstinence at 6-months. Based on a similar prior study, we expect that 6-month point prevalence in the HHC condition will be 6.3%.⁵⁴ For prolonged abstinence, we are basing our estimation on the 2.1% rate for the HHC and 7% rate for SBIRT. We are conservatively estimating a point prevalence cessation rate of 6.3% and prolonged abstinence rate of 2.1% in the HHC group.⁵⁴ We are basing our estimate of 6-month point prevalence of the SBIRT group on the odds ratio derived from meta-analyses assessing the effectiveness of NRT vs. a control, ranging from 1.4-4.6,⁵⁴ to give a cessation rate of 10-12% in the SBIRT group. However, since a clinical counselor/intake coordinator/research coordinator will be conducting the intervention, we expect high compliance in implementation. Thus, we are estimating a cessation rate of 12% in the SBIRT group. Similarly, for prolonged abstinence, we are assuming a rate of 7% in the SBIRT group.

Power (Table 2). Power analyses are based on estimates of differences in both 6-month point prevalence and 6-month prolonged abstinence between groups. With 300 subjects in each group, we would have 80% power to detect an increase of 6.4% in cessation rate. However, assuming a multiple imputation approach, we would be able to detect a 5.5% increase in cessation rate.

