For 6-month abstinence, we can detect an increase of 4.5% with 300 subjects per group and 4.2% with the multiple imputation assumption. These estimates are consistent with the predicted cessation rates shown above and published rates.^{54,93} For analyses based on regression techniques, using hierarchical linear modeling, sample sizes will be more than sufficient. The effect sizes of interest for these analyses are the correlation

Table 2: Estimated Power for varying sample size

N / group	Odds ratio 80% power- prevalence	Odds ratio 80% power- abstinence	Assumption
300	2.16	3.29	20% loss
375	2.00	3.05	Multiple Imputation

coefficients and squared, semi-partial correlations (squared=incremental R^2). To predict caregiver level variables (Primary Aim 1), with a sample size of 750 and 20% lost to follow-up, we will have >80% power to detect a correlation of 0.11 ($r^2=0.013$). For examination of smoking bans (Primary Aim 2), these samples sizes would allow us to detect a difference of 12% with 80% power with 300 per group assuming a rate of between 50% and 65% in the HHC group. Using multiple imputation and 375 per group, we could detect a difference of 11% with 80% power.

Analytic Plan

Data analyses will be conducted at CCHMC and at the University of Cincinnati. A DTA will be established with study investigators at the University of Cincinnati. Data will include demographics, smoking behavior, data from the parent assessments, clinical data, and EMR data. The data will be a limited data set stripped of identifiers. It will be shared on an encrypted file.

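### The assumed point-prevalence effect (6.3% vs 12%, 5.7 points) is smaller than the 6.4 points the plan says 300 per arm can detect; only a row that deducts nothing for dropout covers it

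*Combined protocol and SAP*

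**What the plan says.** All of this is in the combined protocol and SAP, under Sample Size and Power Estimates.

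- **Sample size.** The plan enrols 750 and says that "the sample size must be adjusted for potential attrition of approximately 20% at 6 months", "leaving a total of 600; 300 per group".
- **Assumed effect, point prevalence.** For control, "we expect that 6-month point prevalence in the HHC condition will be 6.3" per cent. For the intervention, "we are estimating a cessation rate of 12% in the SBIRT group".
- **Assumed effect, prolonged abstinence.** 2.1% vs 7%.
- **Detectable effect, point prevalence.** "With 300 subjects in each group, we would have 80% power to detect an increase of 6.4% in cessation rate". Then: "assuming a multiple imputation approach, we would be able to detect a 5.5% increase in cessation rate". Table 2 gives odds ratios of 2.16 at 300 per arm (assumption: 20% loss) and 2.00 at 375 per arm (assumption: multiple imputation).
- **Detectable effect, prolonged abstinence.** "we can detect an increase of 4.5% with 300 subjects per group and 4.2% with the multiple imputation assumption". Table 2 gives odds ratios of 3.29 and 3.05.
- **Conclusion drawn.** "These estimates are consistent with the predicted cessation rates shown above and published rates".

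The primary-aim analysis section names multiple imputation as the main approach. No alpha, sidedness or test is given for the primary comparisons.

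**The concern.** The assumed point-prevalence difference is 12 − 6.3 = 5.7 points. The difference said to be detectable with 80% power at the attrition-adjusted sample size is 6.4 points. The assumed effect is the smaller of the two, so power for it is below 80% at that sample size. The plan nevertheless calls its detectable differences consistent with the predicted rates.

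For point prevalence that is true only on the 375-per-arm row, which uses the whole enrolled sample and so removes the attrition allowance made one paragraph earlier. A careful reader can find the shortfall by subtraction. How much power remains at the assumed effect appears nowhere, and that figure matters when a null result on a primary outcome has to be interpreted.

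**Working it through.** **Inputs (all from Sample Size and Power Estimates).** Control 6.3%, SBIRT 12%; 300 per arm after 20% loss; 375 = 750/2 enrolled per arm; printed detectable differences 6.4 and 5.5 points.

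**1. Text and Table 2 share the 6.3% base.** OR = [q/(1−q)] / [p/(1−p)].
- 6.3% vs 12.7% (+6.4): 2.16, as in Table 2.
- 6.3% vs 11.8% (+5.5): 1.99, against 2.00 in Table 2.
- 6.3% vs 12% (assumed): 2.03, below 2.16.

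**2. Power formula.** With d = q − p, s0 = √[2p̄(1−p̄)] and s1 = √[p(1−p)+q(1−q)], power = Φ[(d√n − z·s0)/s1]. The continuity correction replaces d by d − 1/n.

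**3. Reproducing the printed figures.** Alpha is not stated, so 5% is assumed.

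| Convention | Power, 6.4 points, n=300 | Power, 5.5 points, n=375 |
|---|---|---|
| Two-sided, pooled | 76% | 75% |
| One-sided, continuity-corrected | 81% | 80% |

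The one-sided corrected test comes close to both rows. It also gives 81% for the 4.5-point abstinence figure at 300. It does so at n = 375 with complete data, so the 375 row deducts nothing for missing outcomes.

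**4. Power at the assumed effect, calibrated to the plan.** Choose z so that the plan's own 80% claim holds (pooled test).
- From 6.4 points at 300: s0 = 0.4147, s1 = 0.4122, so z = (0.064×17.321 − 0.8416×0.4122)/0.4147 = 1.837.
- For 6.3% vs 12%: s0 = 0.4077, s1 = 0.4057. Power = Φ[(0.057×17.321 − 1.837×0.4077)/0.4057] = Φ(0.588) = 72%.
- From 5.5 points at 375: z = (0.055×19.365 − 0.8416×0.4039)/0.4057 = 1.787, and power at 300 is 74%.

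The other test forms tried (continuity-corrected, unpooled, arcsine, log-odds) give 71.5% to 72.6% on the first calibration. On the second, the forms run give 73.3% to 73.9%.

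**5. Power at the assumed effect under assumed 5% conventions.** Effective n = 300 + 75r, where r is the share of lost information recovered.

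| Convention | r=0 (300) | r=50% (337.5) | r=100% (375) |
|---|---|---|---|
| Two-sided, pooled | 68% | 73% | 77% |
| One-sided, continuity-corrected | 74% | 79% | 83% |

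At 300 per arm, two-sided continuity-corrected gives 63% and one-sided pooled gives 78%. A one-sided pooled-variance log-odds test reaches 80.3%, but it puts power at 6.4 points at 87%, so it does not match the plan.

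**6. Recovery needed for 80% power.** Calibrated on the 300 row, n = [(1.837×0.4077 + 0.8416×0.4057)/0.057]² = 366; over the test forms the range is 363 to 370, so r = (n − 300)/75 = 84% to 93%. Calibrated on the 375 row, n is 352 to 353 and r is about 70%. Straight interpolation between the two printed rows gives 300 + 75×(6.4−5.7)/(6.4−5.5) = 358, r = 78%.

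**7. Prolonged abstinence.** The assumed 4.9 points (7 − 2.1) exceeds the printed 4.5 at 300 per arm, so the plan's statement holds there. At 375, 2.1% + 4.2 points = 6.3% is OR 3.13, while Table 2's 3.05 corresponds to 4.0 points.

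**The case against.** The best defence is that multiple imputation is the declared primary approach, so the 375 row describes the planned analysis, and 5.7 points exceeds its 5.5. Table 2 labels that assumption openly. Twenty per cent loss is described as a conservative projection. If fewer were lost, more than 300 would be observed: under the one-sided corrected test, 350 per arm suffices, a loss of 25/375, or about 7%. The plan also never claims 80% power for 5.7 points at 300 per arm, and prolonged abstinence is covered.

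Much of this stands. The printed 6.4, 5.5 and 4.5 are not claimed to be miscalculated, and some recovery is plausible because 6-week outcomes enter the models. The smoking-ban calculation also uses 375 with imputation, but it sets no assumed effect against a detectable one, so this point does not reach it.

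The defence does not remove the defect. Imputing a 6-month outcome restores full-sample information only if the predictors determine that outcome almost completely, and nothing in the documents supports this. Better retention is possible, but 20% is the plan's own planning figure, and the plan says the power calculation must allow for it. The 66% recovery implied by 350 per arm, (350 − 300)/75, depends on an assumed test; the plan's own two rows imply about 70% to 93%.

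**Conclusion.** The concern holds. With 300 observed per arm, power for the assumed 6.3% vs 12% is below 80% on the plan's own figures, whatever alpha lies behind them. Calibrated to those figures it is about 72% to 74%, so the chance of missing the assumed effect is about 26% to 28% rather than the 20% that a design with 80% power would carry. Under assumed conventions, power is 68% (two-sided 5%, pooled) or 74% (one-sided 5%, continuity-corrected). Under the two-sided pooled test even full recovery of the dropouts gives only 77%. The claim of consistency with the predicted rates holds for prolonged abstinence at 300 per arm. For point prevalence it needs full or near-full recovery of the lost information. The calibrated results assume 1:1 allocation, exactly 20% loss and a simple comparison of two proportions.

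**What to change.** Under Sample Size and Power Estimates:

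1. State the alpha, sidedness and test behind Table 2.
2. Under that convention, give the power for 6.3% vs 12% at 300 observed per arm: about 68% if two-sided 5% pooled, about 74% if one-sided 5% continuity-corrected.
3. Recompute the four cessation entries on the same basis (80% power, percentage points):

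| Outcome and n per arm | Two-sided, pooled | One-sided, continuity-corrected |
|---|---|---|
| Point prevalence, 300 / 375 | 6.7 / 5.9 | 6.3 / 5.5 |
| Prolonged abstinence, 300 / 375 | 4.7 / 4.1 | 4.5 / 3.8 |

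4. Label the 375 cessation row as an upper bound that assumes no attrition.
5. At 300 per arm, limit the statement of consistency with predicted rates to prolonged abstinence.
6. Reconcile the 4.2-point figure in the text with odds ratio 3.05 in Table 2.

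The smoking-ban figures can stay as they are. The cost is a correction of text and one table; enrolment and analysis do not change. The stated power for point prevalence becomes less favourable.
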